1. INTRODUCTION

This is a randomized, vehicle- and active (triamcinolone 0.1% cream)-controlled study in subjects with mild to moderate AD. The study is double-blinded for vehicle, INCB018424 doses, and active control. Subjects will receive blinded study drug for 8 weeks followed by 4 weeks of optional open-label treatment with INCB018424 1.5% cream BID for subjects who meet Protocol-defined criteria. Section 1 of the Protocol provides a detailed description of the investigational product, target patient population, rationale for doses to be examined, and potential risks and benefits of treatment with INCB018424 cream. The purpose of this SAP is to define the methodology for analyzing and summarizing the data collected during the conduct of Study INCB 18424-206. The scope of this plan includes the interim and final analyses that are planned and will be executed by the Department of Biostatistics or designee [REDACTED]

2. STUDY INFORMATION, OBJECTIVES, AND ENDPOINTS

2.1. Protocol and Case Report Form Version

This SAP is based on INCB 18424-206 Protocol dated 15 SEP 2016, Administrative Change 1 dated 10 JAN 2017, Administrative Change 2 dated 28 MAR 2017, and Administrative Change 3 dated 19 APR 2017, and eCRFs approved 06 FEB 2017. Unless superseded by an amendment, this SAP will be effective for all subsequent Protocol amendments and eCRF versions.

2.2. Study Objectives

2.2.1. Primary Objective

- To establish the efficacy of each dose of INCB018424 cream QD or BID in subjects with AD compared with vehicle cream BID.

2.2.2. Secondary Objectives

2.2.2.1. Key Secondary Objective

- To establish the efficacy of each dose of INCB018424 cream QD or BID in subjects with AD compared with triamcinolone 0.1% cream BID.

2.2.2.2. Other Secondary Objective

- To evaluate the safety and tolerability of INCB018424 cream when applied QD or BID to subjects with AD.

2.3. Study Endpoints

2.3.1. Primary Endpoint

- Mean percentage change from baseline in EASI score at Week 4 in subjects treated with 1.5% INCB018424 cream BID compared with subjects treated with vehicle cream BID.

[figure not shown]
2.3.2. Secondary Endpoints

2.3.2.1. Key Secondary Endpoints

- Mean percentage change from baseline in EASI score at Week 4 in subjects treated with INCB018424 compared with subjects treated with vehicle cream BID.
- Mean percentage change from baseline in EASI score at Week 4 in subjects treated with INCB018424 compared with subjects treated with triamcinolone 0.1% cream BID.

2.3.2.2. Other Secondary Endpoints

- Mean percentage change from baseline in EASI score at Week 2 and Week 8.
- Proportion of subjects who achieve a $\geq 50\%$ improvement from baseline in EASI (EASI-50) at Weeks 2, 4, and 8.
- Assessment of dose response based on percentage change from baseline in EASI score at Week 4.
- Time to achieve EASI-50.
- Proportion of subjects achieving an IGA score of 0 to 1 who have an improvement of ≥ 2 points from baseline at Weeks 2, 4, and 8.
- Mean change from baseline in the Itch NRS score at Weeks 2, 4, and 8.
- Safety and tolerability assessed by monitoring the frequency, duration, and severity of AEs; performing physical examinations; collecting vital signs; and collecting laboratory data for hematology, serum chemistry, and urinalysis.

3. STUDY DESIGN

This is a randomized, vehicle- and active (triamcinolone 0.1% cream)-controlled study in subjects with mild to moderate AD. The study is double-blinded for vehicle, INCB018424 doses, and active control. Approximately 300 subjects will be randomized 1:1:1:1:1:1 (approximately 50 subjects each) to treatment with INCB018424 1.5% BID, INCB018424 1.5% QD, INCB018424 0.5% QD, INCB018424 0.15% QD, vehicle BID, and active control (triamcinolone 0.1% cream) BID and stratified by EASI score (≤ 7 and > 7). Subjects will receive blinded study drug for 8 weeks. Subjects randomized to QD regimens will apply vehicle for the evening application. Subjects randomized to triamcinolone will apply triamcinolone 0.1% cream BID for 4 weeks and vehicle cream for 4 weeks to not exceed the allowable triamcinolone application duration.

After the DB period, a 4-week period of open-label treatment with INCB018424 1.5% cream BID will be offered to subjects who meet Protocol-defined criteria. Subjects will have follow-up assessments 1 month after the last application of study drug. The total duration of participation will be up to 20 weeks, including up to 4 weeks for screening, 8 weeks of DB treatment, 4 weeks of optional open-label treatment, and 4 weeks of safety follow-up.

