5.2. Treatment Groups

This is a study in subjects with AD, with a DB, randomized, and vehicle- and active (triamcinolone 0.1% cream)-controlled treatment period followed by an optional open-label treatment period. Data will be summarized based on the treatment regimen that was initially assigned or that subjects received during the DB period.

- DB period versus open-label period:
 - INCB018424 1.5% BID
 - INCB018424 1.5% QD
 - INCB018424 0.5% QD
 - INCB018424 0.15% QD
 - TAC*
 - Vehicle BID

*Active control (triamcinolone 0.1% cream) BID for 4 weeks followed by vehicle cream BID for 4 weeks.

Table summaries, unless otherwise indicated, will present data by treatment group. The results will be summarized and presented separately for the DB period and open-label period.

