6.4. Exposure

For subjects in the safety population in the DB period and in the open-label evaluable population in the open-label period, descriptive statistics will be provided by treatment group for duration of treatment, average daily dose, and total dose. Duration of treatment with INCB018424 cream, vehicle cream, or triamcinolone cream is defined as the number of days from Day 1 to the last record (defined in [Table 2](#)) of INCB018424 cream, vehicle cream, or triamcinolone cream application.

Table 2: Duration of Treatment

Study Period	Treatment Group	Day 1	Last Record
DB period	All treatment groups	Date of first application in the DB period	Date of last record in the DB period
	INCB018424 cream 1.5% BID	Date of first application in the DB Period	Date of last record in the open-label period
Open-label period	INCB018424 cream 1.5% QD 0.5% QD 0.15% QD Vehicle triamcinolone	Date of first application in the open-label period	Date of last record in the open-label period

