7.4.2. Efficacy Analysis for Other Secondary Endpoints

There will be no adjustment for multiple comparisons for secondary endpoints other than the key secondary endpoints.

[figure not shown]
Mean, change from baseline, and percentage change from baseline of EASI scores to Week 2, Week 4, and Week 8 may be analyzed with the similar MMRM for the primary endpoint. EASI scores at visits other than those covered by the primary and key secondary endpoints will be summarized by treatment and visit using descriptive statistics.

Categorical endpoints, including the percentage of subjects achieving EASI-50 and the percentage of IGA responders at postbaseline visits, will be summarized by treatment and visit using descriptive statistics and may be analyzed by logistic regression with stratification factor of randomization (ie, EASI \leq 7 or $>$ 7). All nonresponders in the DB period, as well as all subjects who discontinue study treatment at any time before the timepoint of interest, or discontinue from the study for any reason, will be defined as nonresponders for the NRI analysis.

An E_{\max} model will be fit for assessment of the dose-response relationship on percentage change from baseline of EASI scores at Week 4, which will provide estimates of the maximum and minimum response levels; ED_{50} (the concentration where the response is the midpoint between the maximum and minimum); and the slope parameter. The 5 dose levels of INCB018424 cream in the model fitting will be vehicle, 0.15% QD, 0.5% QD, 1.5% QD, and 1.5% BID (equivalent to 3% QD).

The Kaplan-Meier product limit method will be used to estimate time to EASI-50. Treatment comparisons may be performed using the log-rank test stratified by randomization stratification factor, if applicable.

Daily Itch NRS scores will be summarized by treatment and visit using descriptive statistics as a continuous endpoint. Itch NRS scores for baseline and Weeks 2, 4, 8, 10, and 12 will be determined by averaging the daily NRS for the days from the start to the end of window as described in [Section 7.2.2](#). In addition, daily NRS Itch scores, from Day -7 to Week 4 will be summarized by treatment group and presented graphically.

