8.2. Adverse Events

8.2.1. Adverse Event Definitions

A TEAE is any AE either reported for the first time or worsening of a pre-existing event after the first application of study treatment. Adverse events will be considered treatment-emergent if they first occurred or worsened in severity after the first application of study treatment and on or before the date of the last visit of the period. Maximum severity from previous period(s) will be considered as the baseline severity for TEAEs.

Treatment-emergent AEs will be allocated to the study period (DB or open-label) according to the rules specified in [Table 5](#).

Table 5: Allocation of Treatment-Emergent Adverse Events to Study Period

Study Period	Treatment Group	First Application Date	Last Visit	Identification of Maximum Severity
DB period	All groups	Date of first application	Date of last visit in DB period	Maximum severity from baseline
Open-label period	INCB018424 cream 1.5% BID	Date of first application in DB period	Date of last visit in open-label period	Maximum severity from baseline
	INCB018424 cream 1.5% QD 0.5% QD 0.15% QD Vehicle triamcinolone	Date of first application in the open-label period	Date of last visit in open-label period	Maximum severity from baseline and DB period

Analysis of AEs (as discussed below) will be limited to TEAEs, but data listings will include all AEs regardless of their timing in relation to study treatment.

Adverse events will be tabulated by MedDRA PT and SOC. Severity of AEs will be described and graded using the NCI CTCAE v4.03. The CTCAE reporting guidelines and grading details are available on the Cancer Therapy Evaluation Program website.

Adverse events will be tabulated by the MedDRA PT and SOC. A grading (severity) scale is provided for each AE term as follows: (1) mild, (2) moderate, (3) severe.

The subset of AEs considered by the investigator to be related to study treatment (INCB018424 cream, vehicle cream, or triamcinolone cream) will be considered to be treatment-related AEs. If the investigator does not specify the relationship of the AE to study medication, the AE will be considered to be treatment-related. The incidence of AEs and treatment-related AEs will be tabulated. In addition, SAEs will be tabulated.

Any missing onset date, causality, or severity must be queried for resolution. Unresolved missing values will be handled according to the following rules:

- An unresolved missing causality will be considered treatment-related.

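### Exposure, adverse events and time to EASI-50 in the triamcinolone arm run through Week 8 with no split at the Week 4 switch to vehicle

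*SAP*

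**What the plan says.** The double-blind period is the same length for everyone: "Subjects will receive blinded study drug for 8 weeks" (SAP Section 3), with "approximately 50 subjects each". The active-control arm changes product halfway: "Subjects randomized to triamcinolone will apply triamcinolone 0.1% cream BID for 4 weeks and vehicle cream for 4 weeks". SAP 5.2 keeps the arm as one group, shown as TAC*: "Data will be summarized based on the treatment regimen that was initially assigned or that subjects received during the DB period". Its footnote reads "Active control (triamcinolone 0.1% cream) BID for 4 weeks followed by vehicle cream BID for 4 weeks". The note to SAP Figure 1 and SAP 6.5 (compliance) repeat the sequence.

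Three sets of output then run through Week 8 without reference to the switch:

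- **Exposure.** SAP 6.4 gives one definition for all creams, ending "triamcinolone cream is defined as the number of days from Day 1 to the last record". Table 2 places that record at the end of the double-blind period for every group. Total and average daily dose are also summarized by group.
- **Adverse events.** SAP 8.2.1 counts events after first application and "on or before the date of the last visit of the period". Table 5 uses the last double-blind visit for all groups. Protocol 9.1 fixes the safety group by the treatment received on Day 1.
- **Time to EASI-50.** SAP 7.2.2 measures it from randomization and states no censoring at the switch. SAP 7.4.2 plans Kaplan-Meier estimates and adds: "Treatment comparisons may be performed using the log-rank test stratified by randomization stratification factor, if applicable".

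SAP Appendix A lists no exposure, adverse event or Kaplan-Meier output restricted to the first 4 weeks. The alpha-controlled tests against triamcinolone (SAP 3.2 and 7.4.1) all use percentage change in EASI at Week 4.

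**The concern.** In these outputs the column headed TAC* mixes 4 weeks of triamcinolone with 4 weeks of vehicle. Duration and dose absorb vehicle use, adverse events that begin on vehicle are counted with those that begin on triamcinolone, and a first EASI-50 response at Week 8 counts as an event for the active control although the subject has been on vehicle since Week 4.

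Safety and tolerability is a stated secondary objective. The key secondary objective compares each dose with triamcinolone, but only 1.5% BID and 1.5% QD have formal tests against it. For 0.5% QD and 0.15% QD, that comparison rests on the descriptive and optional outputs, including the time-to-response curves. At stake is whether the report can compare INCB018424 with triamcinolone over a period when both are actually being applied.

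**Working it through.** The plan states no figure on this point, so there is none to reproduce. Three checks follow.

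**1. Exposure.** Inputs: 4 + 4 weeks and about 50 subjects per arm (SAP Section 3); last double-blind record (SAP Table 2).

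- On triamcinolone: 4 × 7 = 28 days; 50 × 28 = 1400 subject-days.
- Counted under Table 2: 8 × 7 = 56 days; 50 × 56 = 2800 subject-days.
- Ratio: 56 / 28 = 2.

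These are nominal. Visit windows (Protocol Table 2) allow ±3 days at Week 4 and ±7 at Week 8.

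**2. Adverse events.** The documents give no event rates, so only the structure can be shown. With assumed independent 4-week risks p1 and p2, the 8-week risk is 1 − (1 − p1)(1 − p2).

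- Assume 20% on triamcinolone and 10% on vehicle. The arm shows 1 − 0.8 × 0.9 = 28%; a drug with triamcinolone's 20% risk in both halves shows 1 − 0.8² = 36%.
- Reverse the two risks. The arm still shows 28%; a drug with triamcinolone's 10% risk in both halves shows 1 − 0.9² = 19%.

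The sign changes with the assumption, so neither direction nor size can be derived from the documents.

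**3. Time to EASI-50.** Scheduled post-baseline double-blind visits are at Weeks 2, 4 and 8, so only Week 8 (and any unscheduled visit after the switch) is affected. Using the Protocol Table 5 means and SD of 13 points in a normal model, the proportion at EASI-50 by Week 4 is Φ((mean − 50)/13):

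| Arm | Mean | At EASI-50 by Week 4 | Still at risk, of 50 |
|---|---|---|---|
| Triamcinolone | 50 | 50% | 25 |
| 1.5% BID | 75 | 97.3% | 1.4 |
| 1.5% QD | 65 | 87.6% | 6.2 |
| 0.5% QD | 50 | 50% | 25 |

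A log-rank test against triamcinolone was then simulated: unstratified, 50 per arm, 4000 runs, two-sided 5%. Assumptions not in the documents: half of the Week 4 responders respond by Week 2; 50% of remaining INCB018424 nonresponders respond by Week 8; and 0%, 25% or 50% of remaining triamcinolone-arm nonresponders do so. Rejection rates:

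| Arm against triamcinolone | Uncensored, 0% | Uncensored, 25% | Uncensored, 50% | Censored at Week 4 |
|---|---|---|---|---|
| 1.5% BID | 100% | 100% | 99.9% | 100% |
| 1.5% QD | 99.6% | 98.2% | 95.5% | 97.3–97.7% |
| 0.5% QD | 45.9% | 14.6% | 5.4% | 5.2–5.3% |

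The uncensored columns give the assumed late response in the triamcinolone arm. In Table 5, 0.5% QD has the same mean as triamcinolone, so through Week 4 there is nothing to detect. Any rejection above about 5% comes from Week 8, when that arm is on vehicle.

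**The case against.** The case against is substantial, and most of it stands as a limit on the point.

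- A reader might infer that comparisons with the active control are distorted in general. They are not. All four alpha-controlled tests against triamcinolone are at Week 4, before the switch. EASI, EASI-50, IGA, laboratory and vital-sign results are summarized by visit, so comparisons during triamcinolone use exist at Weeks 2 and 4.
- A reader might infer that the SAP presents 8 weeks of triamcinolone. It does not: the group is footnoted as a sequence. As the duration of an assigned regimen, 56 days is correct. The QD arms also include a daily vehicle application under a single regimen label.
- Planned double-blind follow-up is equal across arms, so 8-week adverse event percentages are a valid comparison of regimens as assigned, and events after triamcinolone stops belong to that regimen's profile.
- The log-rank test is optional, outside the alpha-controlled family and not tied to triamcinolone. Kaplan-Meier estimates at Weeks 2 and 4 do not depend on later events. The 46% figure is the extreme of an assumed range.
- A ban on Week 8 comparisons with this arm would go too far, because they are legitimate comparisons with the assigned sequence.

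What the objection does not answer is that the footnote alters no window, dose calculation or censoring rule. The SAP does handle one treatment switch explicitly: on entry to open-label treatment, Tables 1, 2 and 5 restart the clock for every arm except 1.5% BID. It has no corresponding rule for the scheduled switch at Week 4.

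**Conclusion.** The point holds in a limited form. The plan provides no exposure, adverse event or log-rank comparison with triamcinolone confined to the time it is applied, and nominal duration in that arm is twice the time on triamcinolone (56 against 28 days). No confirmatory conclusion is threatened.

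For adverse events, the documents support no statement about the size or direction of any distortion. For time to EASI-50, the two 1.5% comparisons change little. A dose equal to triamcinolone through Week 4 would be declared different in 5% to 46% of trials without censoring, against 5% with it. That range rests on the Table 5 means, the SD of 13 and the assumed response rates after Week 4; when late response is equal in both arms, the excess disappears. This is a worthwhile, inexpensive improvement to the SAP.

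**What to change.** Keep the 8-week tables and make these changes:

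- **SAP 6.4 and 8.2:** add exposure and treatment-emergent adverse event tables limited to Day 1 through the Week 4 visit, for all arms.
- **SAP 6.4:** report the triamcinolone arm's duration and dose separately for the triamcinolone and vehicle phases, using tubes dispensed before the Week 4 visit and from that visit onward. Protocol Table 2 has tubes collected and dispensed at Week 4, and Protocol 4.2 places collection before, and dispensing after, the other assessments, so the visit is a clean cut.
- **SAP 7.4.2:** censor any log-rank comparison of time to EASI-50 with triamcinolone at the Week 4 visit.
- **All Week 8 outputs:** label any comparison with this arm as one with triamcinolone followed by 4 weeks of vehicle.

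The cost is a few extra tables and less follow-up in the time-to-EASI-50 comparison with triamcinolone. No new visits or assessments are needed, but the sponsor should confirm that tube weights are stored by visit so that dose can be split. Setting the rule now avoids choosing it after unblinding.

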3.1. Randomization

In the treatment period, approximately 300 subjects will be randomized 1:1:1:1:1:1 to the 6 treatment groups. Subjects will be stratified at randomization based on baseline EASI score of ≤ 7 or > 7 .

[figure not shown]
3.2. Control of Type I Error

For the primary endpoint and key secondary endpoints, the overall 2-sided Type I error rate is 0.05.

A graphical procedure with a gatekeeping testing strategy for the primary and key secondary analyses, as specified in Protocol Section 9.2.1, will be implemented to control the overall Type I error rate. The underlying procedure is derived using the methodology developed in Bretz et al (2009). This method will guarantee a strong control of the FWER.

A family of 7 elementary hypotheses, corresponding to treatment comparisons between active dose groups and vehicle (or triamcinolone) is evaluated in [Figure 1](#) based on the percentage change from baseline to Week 4 EASI score.

Figure 1: Illustration of the Statistical Treatment Comparisons

AC = active control; s = superiority; ni = noninferiority; V = vehicle.

Note: Active control (triamcinolone 0.1% cream) BID for 4 weeks followed by vehicle cream BID for 4 weeks.

The primary endpoint will test the superiority of INCB018424 1.5% BID compared with vehicle.

The key secondary endpoint has 2 branches. Branch 1 will test whether:

- INCB018424 1.5% BID is noninferior to triamcinolone (active control)
- INCB018424 1.5% QD is noninferior to triamcinolone (active control)
- INCB018424 1.5% BID is superior to triamcinolone (active control)
- INCB018424 1.5% QD is superior to triamcinolone (active control)

Branch 2 will test whether:

- INCB018424 1.5% QD is superior to vehicle
- INCB018424 0.5% QD is superior to vehicle

3.2.1. Primary Analysis

The primary alternative hypothesis (superiority of INCB018424 1.5% BID compared with vehicle) will be tested at a 2-sided $\alpha = 0.05$ level. The test on the primary endpoint will be used as a gatekeeper for 6 statistical tests on secondary endpoints that will be grouped into 2 parallel branches (see [Figure 1](#)). The first branch (Branch 1) includes tests of INCB018424 versus the active control (triamcinolone). The second branch (Branch 2) includes tests of INCB018424 versus vehicle. The initial allocation of the overall significance level to Branch 1 and Branch 2 is 3/5 and 2/5, respectively. The weights of the level to be passed on if 1 hypothesis is rejected are specified in [Figure 1](#).

3.2.2. Secondary Analysis

3.2.2.1. Tests in Branch 1

- **Step 1:** The first alternative hypothesis (noninferiority of INCB018424 1.5% BID compared with triamcinolone) will be tested at a 2-sided $\alpha = 0.03$ level if the primary test is significant. If the first alternative hypothesis is established, then hypotheses in Step 2 will be tested at an overall error rate of 0.03.
- **Step 2:** If Step 1 is established, then a superiority test of INCB018424 1.5% BID compared with triamcinolone and noninferiority test of INCB018424 1.5% QD compared with triamcinolone will be carried out using the Bonferroni-Holm procedure at an overall 2-sided $\alpha = 0.03$ level.
- **Step 3:** If both of the null hypotheses in Step 2 are rejected, then a superiority test of INCB018424 1.5% QD compared with triamcinolone will be carried out at a 2-sided $\alpha = 0.03$ level.

If all 4 tests in Branch 1 are significant, then the overall level ($\alpha = 0.03$) of Branch 1 will be reallocated to Branch 2, and the first alternative hypothesis in Branch 2 will be tested with start level of 2-sided 0.05. If 1 or more of the tests in Branch 1 is nonsignificant, there will be no level reallocated from Branch 1 to Branch 2, and the first alternative hypothesis in Branch 2 will be tested with start level of 2-sided $\alpha = 0.02$.

3.2.2.2. Tests in Branch 2

- Alternative hypotheses (superiority of INCB018424 1.5% QD and 0.5% QD compared with vehicle) will be tested in sequence using the alpha level decided in previous steps.

If 1 or more of the 4 tests in Branch 1 is nonsignificant, but all tests in Branch 2 are significant, then the alpha level will be reallocated to Branch 1, and Branch 1 will reopen with a start level of 2-sided $\alpha = 0.05$.

